7.8.2 Other Immunological Assays

Cytokine, T-cell and B-cell stimulation assays, and PBMC phenotyping may be performed on PBMCs. RNA may be isolated from cells and run on microarrays to identify immune pathways of interest, such as defining the innate immune response to the vaccine virus. In addition, human leukocyte antigen (HLA) typing of samples may be performed as part of assays to map the Zika virus epitopes that induce T- or B-cell responses. In addition, an exploratory neutralization capacity assay may be performed using target cells that express CD32a (Fc γ RIIa). This assay will evaluate the effect of neutralizing and enhancing antibody in the same assay. ZIKV specific antibodies will be measured in oral fluids as an exploratory assay for detection of Zika.

7.9 Retention of Study Subjects

We will employ several strategies aimed at retaining subjects through study completion. During screening, we will obtain detailed primary locator information, as well as secondary contact information. Subjects will also provide information for people who may be contacted if primary and secondary means of contact fail. Locator information will be reviewed with subjects at each visit (i.e., addresses, phone numbers, email addresses). In addition, birthday cards/holiday cards may be mailed to check addresses, and reminders may be sent using various methods (including, but not limited to, phone, email, text messaging, electronic media, and postal mail). All data will be maintained and updated in a password-protected locator database.

8 ADVERSE EVENT MONITORING

8.1 Definitions

8.1.1 Adverse Event

An adverse event (AE) is any untoward or unfavorable medical occurrence in a human subject, including any abnormal sign (e.g., abnormal physical exam or laboratory finding), symptom, or disease, temporally associated with the subject's participation in the research, whether or not it is considered related to the research.

All AEs will be evaluated for severity, action taken, seriousness, outcome, and relationship to the investigational vaccine as described in Section 8.2 in this protocol. If a diagnosis is clinically evident (or subsequently determined), the diagnosis rather than the individual signs and symptoms or lab abnormalities will be recorded as the AE. AEs will be collected through the 28-day period following inoculation, and any test agent-related AEs (adverse reactions, see below) identified in the 28-day post-inoculation period will be followed until resolution.

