- 1) Assess the frequency, quantity, and duration of viremia after a single dose of rZIKV/D4Δ30-713 given at either 10^3 PFU or 10^4 PFU.
- 2) Evaluate the number of vaccine recipients infected with either 10^3 PFU or 10^4 PFU rZIKV/D4Δ30-713. Infection is defined as recovery of infectious vaccine virus from the blood, serum, or urine of a subject and/or by seroconversion to ZIKV (plaque-reduction neutralization titer [PRNT₅₀] $\geq 1:10$) within the 90-day period following vaccination.
- 3) Determine the durability of antibody response 26 weeks after vaccination.
- 4) Determine the quantity and duration of ZIKV presence as determined by:
 - The peak virus titer in the blood and the duration of viremia induced by the LA Zika vaccine as determined by RT-PCR and virus culture
 - The quantity and duration of possible Zika vaccine shedding in urine determined by RT-PCR and virus culture
 - The quantity and duration of possible Zika vaccine shedding in vaginal secretions determined by RT-PCR and virus culture
 - The quantity and duration of possible Zika vaccine shedding in semen determined by RT-PCR and virus culture

Exploratory objectives:

- 1) To evaluate the phenotype of peripheral blood mononuclear cells (PBMCs) at primary infection with the rZIKV/D4Δ30-713 vaccine.
- 2) To evaluate the cellular immune response to primary infection with the rZIKV/D4Δ30-713 vaccine.
- 3) To evaluate the innate immune response to primary infection with the rZIKV/D4Δ30-713 vaccine.
- 4) To evaluate B and T cell memory responses following primary infection with the rZIKV/D4Δ30-713 vaccine.
- 5) To evaluate the antibody response in saliva to infection with rZIKV/D4Δ30-713 as a possible diagnostic tool. This will be done in a subset of subjects (those enrolled at the Center for Immunization Research [CIR]).

Primary Endpoints

Safety

Occurrence, intensity and relationship to vaccination of solicited local and general adverse events (AEs) within the 28-day follow-up period after vaccination.

Occurrence, intensity and relationship to vaccination of unsolicited AEs within the 28-day (Days 0-28) follow-up period after vaccination.

Occurrence of medically-attended adverse events and serious adverse events (SAEs) throughout the entire study period.

Immunogenicity

Determination of the peak neutralizing antibody titer to ZIKV through 90 days following vaccination with either 10^3 PFU or 10^4 PFU of rZIKV/D4 Δ 30.

Secondary Endpoint

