7.5 Subject Temperature Memory Card

Subjects will be provided with a thermometer and a Temperature Memory Card to use as a memory aid and will be asked to record temperatures 2 times a day from study day 0 through study day 16 post-inoculation. Study staff will review the subjects' temperature cards on study day visits 4 through 21 to assess for any fevers and compare subject recordings to the study visit temperatures. Staff will record all temperatures recorded by the subject and will also separately record the maximum temperature for each date (T_{max}) on the source document. Subject memory cards will not be collected by the study staff as subject's recordings will not be considered required data.

Staff will instruct subjects on how to use the thermometers, to take their temperatures at approximately the same time each day, and to take additional temperatures if they feel they have elevated temperatures. Subjects will be asked to wait at least 15 minutes after eating, drinking, and smoking before taking their temperatures. They will be asked to confirm an elevated temperature ($\geq 100.4^{\circ}\text{F}$) by retaking the temperature after a 20-minute interval and at 1 hour. Temperatures not documented to last at least 1 hour will not be considered an AE or included in the analysis.

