8.2 Assessment of Adverse Events

8.2.1 Identification of Adverse Events

All AEs occurring from the time the subject is enrolled (at administration of investigational agent on day 0) through the Study Day 28 will be documented, recorded, and reported. The Investigator will assess all AEs with respect to **Seriousness**, **Severity**, and **Causality** (relationship to study agent and relationship to research) according to the following guidelines. An assessment of safety will include clinical observations and monitoring of hematological, blood chemistry, and immunologic parameters. Safety will be evaluated by monitoring the subjects for local and systemic adverse events during the course of the trial. Subjects will be closely monitored for 30 minutes following inoculation. Additionally, subjects will return to the clinic on study days 4, 6, 8, 10, 12, 14, 16, 21, and 28 post-inoculation and may be asked to return more often if warranted. It is during this time period that we anticipate AEs related to infection with the vaccine virus to manifest themselves; therefore, the subjects will be seen frequently. Study staff will review subjects' reported temperatures and clinical temperatures for the first 16 days following inoculation to assess for AEs. At each visit through study day 28 following inoculation, subjects will be queried about adverse events, including possible vaccine-related AEs (solicited AEs) and will have a focused physical exam performed. A study clinician will be available to subjects by telephone or pager 24 hours a day during the study evaluation period.

All AEs will be recorded during the period after the subject receives the study vaccine through and including post-inoculation study day 28.

All SAEs will be assessed appropriately as AEs and reported following SAE reporting guidelines outlined in Section 8.3.2 of this protocol.

8.2.2 *Protocol Specific Adverse Event Definitions*

Fever: Temperature $\geq 100.4^{\circ}\text{F}$ lasting at least 1 hour

ZIKV-like Rash: Areas of **confluent** macular or maculo-papular rash over trunk and extremities, blanches when compressed.

Non-purulent conjunctivitis: Bilateral reddening of the sclera of the eyes without evidence of exudate or crusting of the eyelids

Headache: A pain located in the head, over the eyes, at the temples, or at the base of the skull.

ROP: Bilateral pain situated behind the orbits of the eye

Photophobia: An abnormal sensitivity or intolerance to light

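### Two recording rules can understate solicited reaction rates: a diagnosis replaces its symptoms, and an elevated temperature with no one-hour reading counts as no fever

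*Combined protocol and SAP*

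**What the plan says.** **Diagnosis rule.** Section 8.1.1 applies to all AEs. Once a diagnosis is made, at the time or later, "the diagnosis rather than the individual signs and symptoms or lab abnormalities will be recorded as the AE". Table 9 in Section 8.1.3 lists the solicited events, and they are just such signs, symptoms and laboratory findings. Neither that section nor Sections 8.2 or 10 exempts them.

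**Fever rule.** Section 7.5 asks the subject to confirm an elevated temperature (100.4°F or above) "by retaking the temperature after a 20-minute interval and at 1 hour". It then states: "Temperatures not documented to last at least 1 hour will not be considered an AE or included in the analysis". The card is not collected, and the "subject's recordings will not be considered required data", although staff copy every reading and the daily maximum to source. Section 8.2.2 likewise defines fever as a temperature at or above 100.4°F "lasting at least 1 hour".

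**What the rules feed.** The Precis lists as one primary safety endpoint "Occurrence, intensity and relationship to vaccination of solicited local and general adverse events (AEs) within the 28-day follow-up period after vaccination", and as another "Occurrence, intensity and relationship to vaccination of unsolicited AEs within the 28-day (Days 0-28) follow-up period after vaccination". Section 10.3 counts vaccine-related AEs. Section 10.2 describes the trial as estimating event frequencies, without formal tests. Halting criterion 8 in Section 8.5.1.1 needs fever together with the grade and duration of individual symptoms.

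**The concern.** Solicited rates are one of the main outputs of a first-in-human trial of a live vaccine, and each rule can lower them.

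The protocol itself generates diagnoses. Subjects with COVID-like symptoms are swabbed, and swabs may also be taken on Days 8 and 14. Under Section 8.1.1, a positive result would take the accompanying headache, fatigue or myalgia out of its own row.

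Under Section 7.5, a missing one-hour reading has the same effect as a reading that shows the fever had gone. For home readings the repeat is left to the subject. The visit lists in Section 7.4.1 call for vital signs but for no one-hour repeat, so an elevated clinic temperature has the same gap.

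The stake is the absolute rate reported for each dose, and whether the data behind halting criterion 8 are kept in a usable form.

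**Working it through.** **1. The rules side by side.**

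| Situation | Solicited row | Elsewhere |
|---|---|---|
| Table 9 symptom, no diagnosis | Counted | – |
| Table 9 symptom under a diagnosis judged related | Not counted | AE under the diagnosis; in the Section 10.3 count |
| Table 9 symptom under a diagnosis judged unrelated | Not counted | AE under the diagnosis; not in the Section 10.3 count |
| Elevated temperature, one-hour reading also elevated | Fever | – |
| Elevated temperature, shown to last under one hour | Not fever, by Section 8.2.2 | Source only |
| Elevated temperature, no one-hour reading | Treated as no fever | Source only |

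Rows 2, 3 and 6 carry the point. Row 5 agrees with the protocol's own definition.

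**2. The plan's own figures.** The documents give no figure for the effect of either rule. The nearest figures are the Cohort 1 results in Table 7. Its percentages convert to counts out of 20 and 8: headache 10/20 v 5/8, myalgia 4/20 v 2/8, fever 0/20 v 0/8. A one-sided Fisher exact test on these counts gives 0.8454 for headache and 0.7922 for myalgia, as printed. The other five printed P values also reproduce to four decimals. Table 7 therefore counts subjects symptom by symptom on denominators of 20 and 8.

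**3. Size of one affected subject.** 1/20 = 5 points in a vaccine group and 1/8 = 12.5 points in a placebo group. One replaced headache in Cohort 1 would turn 10/20 (50%) into 9/20 (45%).

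**4. Fever with missing repeats.** Let p be the true rate of fever as the protocol defines it, and c the share of those fevers with a documented one-hour reading. Both are assumptions; the documents give neither. The expected recorded rate is p × c. The chance of recording no fever in 20 vaccinees is (1 − pc)^20:

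| p | c = 1 | c = 0.75 | c = 0.5 |
|---|---|---|---|
| 5% | 36% | 47% | 60% |
| 10% | 12% | 21% | 36% |
| 20% | 1.2% | 3.9% | 12% |

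For p = 10%: 0.90^20 = 0.122, 0.925^20 = 0.210, 0.95^20 = 0.358.

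**5. Reading the Cohort 1 zero.** For 0/20 the exact two-sided 95% upper limit is 1 − 0.025^(1/20) = 16.8%. That limits the recorded rate pc. The limit on p is 16.8%/c: 16.8% at c = 1, 22.5% at c = 0.75 and 33.7% at c = 0.5.

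**6. Both arms.** If c is the same in both arms, each rate is multiplied by c and so is their difference: c·p(vaccine) − c·p(placebo) = c·[p(vaccine) − p(placebo)]. Equal application keeps the comparison from favouring one arm but does not restore the absolute rates.

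**The case against.** A good case can be made for leaving the text alone. Section 8.2.2 builds the one-hour duration into the definition of fever, so Section 7.5 largely applies that definition. Staff review the card at visits from Day 4 to Day 21 and copy all readings and the daily maximum to source, so an unconfirmed reading can be retrieved. Solicited events are queried at every visit through Day 28 and graded one by one, and Table 7 shows them tabulated separately. Criterion 8 turns on what subjects experience, not on the recorded AE term. For confirmed COVID-19, recording the diagnosis is a defensible choice.

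Most of this stands, and it limits the point. It does not answer the two gaps: no text says that Table 9 events survive a diagnosis, and no text separates an unmeasured hour from a fever that had resolved.

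Three stronger readings are tempting, and the documents do not support them:

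- *A reader might infer that reactions are deleted from the primary safety endpoint.* A diagnosed event stays an AE with its grade and causality, and unsolicited AEs are also a primary endpoint. It changes row.
- *A reader might infer that fever goes unobserved after Day 16*, because subjects "will be asked to record temperatures 2 times a day from study day 0 through study day 16 post-inoculation". Vital signs are taken on Days 21 and 28, solicited events are queried through Day 28, and subjects are asked to report Table 9 systemic signs. Section 5.4.1 expects vaccine virus replication through Day 16.
- *A reader might infer that the loss is greatest in the strongest reactors.* Nothing in the documents shows that they are diagnosed more often, or repeat their temperature less often.

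**Conclusion.** The point holds as a defect in the recording and analysis rules and should be corrected. Followed as written, Section 8.1.1 moves a solicited symptom under a named diagnosis out of the solicited tabulation, and Section 7.5 counts an elevated temperature with no one-hour reading as no fever. Both can understate absolute solicited rates in both blinded arms; no bias towards one arm is shown.

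The size is unknown. The documents do not say how often symptoms are replaced by a diagnosis or how often the repeat is missing. What is certain is the unit, 5 points per vaccinee in a group of 20. The zero-fever probabilities and the widened upper limits rest on assumed values of p and c, and on c being the same for every fever. They show sensitivity; they do not show that any Cohort 1 fever was missed.

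**What to change.** 1. In Section 8.1.1, state that Table 9 events are recorded and tabulated under their own term, grade and day, in addition to any diagnosis.
2. In Sections 7.5 and 10, keep the protocol's fever definition for the main row. Add a sensitivity row and a listing, by arm and cohort, of temperatures at or above 100.4°F with no one-hour reading, whether taken at home or in clinic. Show readings documented to have resolved within the hour apart from these.
3. Reconcile Sections 7.5, 8.1.1, 8.2.2 and 8.5.1.1, so that the fever status and the symptom-level grade and duration needed for halting criterion 8 are kept when a diagnosis is recorded. The clinical definition of fever stays with the sponsor.

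The cost is about two sentences, one table row and one listing. No new collection is needed for the fever row, because the readings and daily maxima are already copied to source. The drawback is a few spurious single readings, which are confined to the sensitivity row.

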8.1.2 Medically-attended Adverse Event

A medically attended AE is defined as any visit (other than hospitalization, visit for routine health maintenance, or visit for a pre-existing condition that has not worsened) to an emergency room (ER), urgent care facility, doctor, nurse, or any other health care provider. Medically attended AEs from days 29 through 180 will be collected. Medically attended AEs that are found to be unrelated to the study product will be followed until resolution or the end of the study, whichever occurs first.

8.1.3 Adverse Reaction

An adverse reaction (AR) is an AE that is caused by an investigational agent (drug or biologic). AEs that are deemed possibly, probably, or definitely related to study article will be classified as adverse reactions. ARs are categorized as solicited ARs and other ARs. Solicited ARs include local reactogenicity, systemic reactogenicity, and laboratory events. Solicited ARs are those events that the clinician is specifically evaluating during the 28-day post-inoculation period, listed in [Table 9](#). All AEs are evaluated using the Adverse Event Grading Table in Section [14.1](#), [Appendix 1](#).

Table 9: Solicited Adverse Events/Adverse Reactions

Systemic Reactogenicity	Laboratory Events	Local Reactogenicity
Fever	Decreased Hemoglobin	Injection Site Pain
Headache	Neutropenia	Injection Site Erythema
Retro-orbital Pain (ROP)	Elevated ALT	Injection Site Tenderness
Photophobia	Thrombocytopenia	Injection Site Induration
Nausea	Leukocytosis	Injection Site Pruritus
Fatigue		
Myalgia		
Arthralgia		
Non-purulent Conjunctivitis		
Muscle Weakness		
Zika Virus-Like Rash		

8.1.4 Adverse Event of Special Interest

Guillain-Barré syndrome (GBS) is an AE of special interest. Subjects will be examined for signs of muscular weakness at each visit that includes a physical exam and muscle strength will be reported as in Section [8.2.2](#). Should a subject present to an outside physician for evaluation of GBS, this will be captured and reported. The Brighton Criteria for diagnosis of GBS will be used (Section [14.2](#), [Appendix 2](#)) and the WHO Guillain-Barré Syndrome Disability Scale will be used (Section [14.3](#), [Appendix 3](#)).

8.1.5 Pregnancy

Pregnancy itself is not an AE. However, complications of pregnancies are AEs and may be serious adverse events (SAEs). Events that meet SAE criteria during pregnancy, delivery, or in the neonate (e.g., congenital anomaly/birth defect) are reportable to the Clinical Safety Office (CSO) per the sponsor's reporting guidelines. Pertinent obstetrical information for all

pregnancies will be reported to the CSO via the REDCap reporting system within 1 business day from site awareness of the pregnancy on the Pregnancy Notification and Outcome Form.

Pregnancy outcome data (e.g., delivery outcome, spontaneous or elective termination of the pregnancy) will be reported to the CSO within 3 business days of the site's awareness on a protocol-specified form. If a subject becomes pregnant within 28 days of test article administration, the subject will be unblinded to determine if she received ZIKV. If she did receive ZIKV, she will be referred to an OB/GYN experienced in caring for ZIKV-infected pregnant women ([name] at JHU).

If the pregnancy occurs prior to study day 28 after rZIKV/D4Δ30-713 administration, as determined by a positive pregnancy test at the study day 28 visit or before, the subject will not be included in the per-protocol analysis. The subject will remain on the study for safety follow-up.

- If unblinding the treatment assignment would help the subject determine whether she wishes to continue her pregnancy, her treatment assignment will be unblinded.
- The research subject will be advised to notify her obstetrician of study participation and study agent exposure.
- The pregnancy will be reported to the DSMB (if applicable) and/or IRB (if applicable).

If the pregnancy occurs after study day 28 following rZIKV/D4Δ30-713 administration, as determined by a positive pregnancy test after the study day 28 visit, the subject will be included in the per-protocol immunogenicity analysis.

8.1.6 Serious Adverse Event

A serious adverse event (SAE) is an AE that is determined to be “serious,” whether considered related to the investigational vaccine or not. SAEs will be collected for the duration of the trial. An SAE results in one or more of the following outcomes:

- Death during the period of protocol-defined surveillance
- A life-threatening event, defined as an event that places a subject at immediate risk of death at the time of the event and does not refer to an event that hypothetically might have caused death were it more severe
- Inpatient hospitalization or prolongation of existing hospitalization, defined as at least an overnight stay in the hospital or emergency room for treatment that would have been inappropriate if administered in the outpatient setting
- Congenital anomaly or birth defect
- Persistent or significant incapacity or substantial disruption of the ability to conduct normal life functions
- Other medically important events*

*Medical and scientific judgment should be exercised in deciding whether expedited reporting is appropriate in other situations, such as important medical events that may not be immediately

life-threatening or result in death or hospitalization but may jeopardize the subject or may require intervention to prevent one of the outcomes listed above. These will also usually be considered serious.

Each AE will be classified by the investigator/designee as serious or non-serious. An SAE needs to meet only one or more of the above criteria to be considered serious.

8.1.7 Unexpected Adverse Events

An AE is considered unexpected if it is not listed in the Investigator's Brochure or Package Insert (for marketed products) or is not listed at the specificity or severity that has been observed. "Expected" does not mean that the event is expected with pharmacologically similar drugs, the underlying disease(s), or concomitant medications. It is the responsibility of the IND sponsor to make this determination.

8.1.8 Serious and Unexpected Suspected Adverse Reaction (SUSAR)

A serious and unexpected suspected adverse reaction (SUSAR) is a suspected adverse reaction (SAR) that is serious and unexpected.

8.1.9 Unanticipated Problem

An unanticipated problem is any event, incident, experience, or outcome that is:

1. Unexpected in terms of nature, severity, or frequency in relation to
 - a. The research including but not limited to risks that are described in the IRB-approved research protocol and informed consent document; Investigator's Brochure or other study documents; and
 - b. The characteristics of the subject population being studied;
2. Possibly, probably, or definitely related to participation in the research; and
3. Places subjects or others at a greater risk of harm (including physical, psychological, economic, or social) than was previously known or recognized. (An AE with a serious outcome will be considered increased risk).

